6 AMENDMENTS AND UPDATES

None (original protocol).

20 of 130

7 MILESTONES

Study milestones are summarised in Table 1.

Data collection (this refers to first data extraction) is expected to start on 31 May 2025. This start date considers the duration of time required to process all required ethics and data access applications in the countries of interest. This time may vary between approximately 7 and 18 months.

Study progress will be reported in the Periodic Safety Update Reports and will contain patient counts for the available data sources and any relevant amendments required for database applications. A preliminary assessment of the assumptions of anifrolumab uptake will be conducted to address the need of mitigation plans such as the inclusion of additional data sources or extension of the study time period.

One joint interim report (Interim report 1 SI & M) will be submitted for the *serious infections* and *malignancy* outcomes on 31 May 2027. Another interim report (Interim report 2 M) will be submitted exclusively for the *malignancy* outcome on 31 May 2030. Interim report 1 will contain descriptive analyses relevant to primary and secondary objectives, only for those data sources for which relevant data are available for reporting. The assumptions of anifrolumab uptake will be re-assessed to evaluate the feasibility of the final study report milestones. If the assumptions do not hold, mitigation steps will be explored.

The second interim report is related to *malignancy outcomes* and will be submitted 36 months after the first interim report. It will contain descriptive analyses relevant to primary and secondary objectives, only for those data sources for which relevant data are available for the reporting.

The final study reports are planned¹ for 30 November 2028 for *serious infections outcomes* and for 30 November 2032 for *malignancy outcomes*, provided that required sample sizes are reached at that time. It is estimated that the required sample size of 1,312 anifrolumab users for the serious infections outcomes, and 3,195 anifrolumab users for the malignancies outcome (see Section 10.5.2) will be attained, under the assumption that anifrolumab uptake will increase during the study period from less than 1% to ~16% at the end of the study enrolment (see Section 10.5.1 and Table 27 for further details on the estimated number of annual anifrolumab users in each data source). However, these assumptions of anifrolumab uptake will be assessed at the progress report and the first interim report to confirm the milestones for the final study reports. The final study reports will include all descriptive, comparative, exploratory, sensitivity analyses and meta-analysis for all the data sources for the outcomes of interest.

¹ Assuming protocol approval by PRAC on 31st August 2023.

Table 1 Study milestones

Milestone	Planned date ^a
PRAC approval	31 August 2023 ^b
Registration in the EU PAS register	30 November 2023
Start of data collection ^c	31 May 2025
Interim report 1 (SI & M)	31 May 2027
Final report of study results (SI)	30 November 2028
Interim report 2 (M)	31 May 2030
End of data collection ^d	30 November 2031
Final report of study results (M)	30 November 2032

^aSchedule is dependent on the date of protocol approval by PRAC. Any deviations from this tentative date may lead to an amendment of all subsequent dates.

^bThis is a tentative date and will be revised to reflect actual date of approval if needed.

^cDate at which data extraction starts.

^dDate at which the analytical dataset is completely available.

Abbreviations: EU PAS - European Union electronic Register of Post-Authorisation Studies; PRAC - Pharmacovigilance Risk Assessment Committee SI - Serious Infections Outcomes; M – Malignancies Outcomes

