Considering the estimated sample size required for this study, it is anticipated that the selected data sources will provide the sufficient sample size required to address the research questions (see Section 10.5). If it is determined at the time of interim reports, that the selected data sources will not provide the required sample size, mitigation approaches will be considered. These mitigation approaches include the use of additional data sources (which were deemed feasible but not currently selected), and extension of the study period.

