10.5.2 Minimum sample size required

As the main analysis for the primary outcomes (i.e., serious infections and malignancies) will involve a meta-analysis pooling the estimates across all data sources, a meta-analytic approach in sample size estimation was used for each outcome separately. Simulations were used to compute the estimated power to detect pre-specified HR values representing the average population treatment effect (mean) for the anifrolumab exposed group compared to the unexposed group for pre-specified sample sizes. In addition, the minimum sample sizes required to achieve 80% power under specific assumptions were estimated.

⁸ The number of SLE patients provided by the data sources is slightly higher than the estimated average. Thus, current estimates are expected to be a conservative measure of the number of included patients. At the time of interim reports, the number of SLE patients and the assumptions of anifrolumab uptake will be assessed to address the need of protocol adjustments to meet the necessary sample size.

Assumptions and parameters

The main objective of this study is to estimate and compare the risks between the study cohorts in terms of two outcomes – serious infections and malignancies.

Keeping this in mind, the sample analysis methodology relies on estimating power to detect any treatment associated risks between the study cohorts. In this case, we assumed pre-specified HR values of 1.5, 1.8 and 2, as the average population treatment effect (mean) and for variability of this HR, we use two values of assumed standard deviation, 0.1 and 0.2. The idea here is to have a population-level treatment effect distribution of HR with mean values of 1.5 or 1.8 or 2.0, such that from this distribution, every data source randomly samples a unique HR value per simulation run. This approach ensures the variability and heterogeneity which we expect to see from data sources which then necessitates the use of random effects meta-analysis to account for them during the final analysis of this study. Two matching ratios of exposed to non-exposed, 1:1 and 1:3, were chosen. Background rates for the primary outcomes were also varied based on published literature of incidence in the general population and in an SLE population.

Background rates

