Considering the estimated number of patients initiating anifrolumab during the study period (3,506 for the malignancies cohort, and 1,435 for the serious infections cohort Table 8) and the required sample size presented above (3,195 for the malignancies cohort and 1,312 for the serious infections

cohort), there is a reasonable assumption that the final study report milestones as specified in this protocol can be met. However, the assumptions used in the calculation of the exposed anifrolumab patients will be evaluated at the first progress report (31 May 2026) and first interim report (31 May 2027). If the assumptions do not hold, the final study report milestones will be re-evaluated, and potential mitigation steps will be explored.

each data source)											
Country	Share of	Minimum required sample size	Minimum required sample size								
	country in	(anifrolumab patients) for the	(anifrolumab patients) for the SI								
	study (%)	Malignancy outcome with IR = 6.31	outcome with IR = 39.8 per 1000 py								
		per 1000 py									
Denmark	5.89%	188	77								
France	74.56%	2,382	978								
Germany	5.40%	173	71								
Spain	14.16%	452	186								
Total	100.00%	3,195	1,312								

Table 13 Minimum sample size needed for malignancy and SI outcomes (overall and in each data source)

Abbreviation - HR: hazard ratio; IR: incidence rate; SD: standard deviation

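### The study-size check counts anifrolumab users only, so it can be passed with about 200 events per outcome and about 60% power, not the roughly 450 events and 80% power behind the targets

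*Protocol*

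**What the plan says.** Section 7 plans the final reports for set dates "provided that required sample sizes are reached at that time", and defines that condition as "the required sample size of 1,312 anifrolumab users for the serious infections outcomes, and 3,195 anifrolumab users for the malignancies outcome". It adds that "these assumptions of anifrolumab uptake will be assessed at the progress report and the first interim report to confirm the milestones" for those reports.

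Section 10.5.2 repeats the re-check in the same terms: "the assumptions used in the calculation of the exposed anifrolumab patients will be evaluated at the first progress report" and again at the first interim report. Footnote 8 widens it slightly: "the number of SLE patients and the assumptions of anifrolumab uptake will be assessed to address the need of protocol adjustments" at the interim reports. That is still a head count.

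Section 10.4 holds the trigger for action: "If it is determined at the time of interim reports, that the selected data sources will not provide the required sample size", mitigation is to be considered. It lists the options: "These mitigation approaches include the use of additional data sources (which were deemed feasible but not currently selected), and extension of the study period".

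None of these places brings observed events, incidence, person-time or achieved matching into the decision. Section 10.5.2 nevertheless derives the two user counts from all of these: HR 1.5 with SD(HR) 0.2, 1:3 matching, incidence of 39.8 (serious infections) and 6.31 (malignancy) per 1,000 person-years, and average follow-up of 2 and 5 years.

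**The concern.** The power of a Cox analysis, and of a random-effects pooling of Cox estimates, is driven by events. A user count stands in for events only while incidence, follow-up and matching stay as assumed. The protocol re-checks the one input it can count early and leaves the others unchecked, although its own calendar already conflicts with the follow-up assumption.

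This is a safety study. If the user count is met and events are fewer than half those planned, a non-significant hazard ratio could be read as reassurance from a study believed to have 80% power.

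The user count also has little room for attrition. The forecasts of 1,435 and 3,506 exceed the targets by 123 and 311 patients, so a loss of 8.6% (123/1,435) or 8.9% (311/3,506) uses up the margin. Appendix 4.3 builds the forecasts from prevalence, non-renal disease, treatment, severity and uptake. It makes no deduction for the flare requirement, prior malignancy, recent serious infection, the 12-month look-back, or exposure sets dropped for positivity (Section 10.7.1.1, step 8).

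**Working it through.** **1. Reproducing the stated sizes.** Inputs from Section 10.5.2 and Table 13: four sources with shares 5.89%, 74.56%, 5.40% and 14.16%; source-level HRs lognormal around 1.5 with log-SD 0.132; 1:3 matching; random-effects inverse-variance pooling; p < 0.05 taken as two-sided. Events were simulated directly in place of the Weibull/Cox fit. Power is 0.77 to 0.81 for both 3,195 and 1,312 users, depending on the heterogeneity estimator and the event approximation. The stated 80% is reproduced.

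**2. Events behind those sizes.** With N exposed, 3N comparators, incidence λ and follow-up t:

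E = N(1 − exp(−1.5λt)) + 3N(1 − exp(−λt))

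- Serious infections, N = 1,312, λ = 0.0398, t = 2: 148 + 301 = 449.
- Malignancy, N = 3,195, λ = 0.00631, t = 5: 148 + 298 = 445.
- At HR 1, E = 4N(1 − exp(−λt)): 402 and 397.

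**3. Follow-up the calendar allows.** Table 27 initiations are summed over sources, with the 2022 cells shown as <10 set to 0, as the table totals imply. Each year's initiators sit at the middle of the part of the year open to enrolment (Table 3), and are followed to 31 May 2025 (serious infections) or to 31 May 2029 less 12 months' latency (malignancy). Nobody discontinues, dies or leaves.

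| Year | Initiators | Mean years, SI | Mean years, malignancy |
|---|---|---|---|
| 2022 | 29 | 2.78 | 5.78 |
| 2023 | 317 | 1.89 | 4.89 |
| 2024 | 460 | 0.91 | 3.91 |
| 2025 | 629 | 0.25 | 2.91 |
| 2026 | 953 | – | 1.91 |
| 2027 | 634 | – | 0.91 |
| 2028 | 484 | – | 0.20 |

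- Serious infections: about 1,254 person-years / 1,435 = 0.87 years.
- Malignancy: about 7,843 person-years / 3,506 = 2.24 years.

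For both outcomes, only patients starting by about the end of May 2023 can reach the assumed average (2 years, or 12 months' latency plus 5 years). Table 27 places at most 29 + 317 = 346 initiators before the end of 2023.

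**4. User targets met exactly, with that follow-up.**

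- Serious infections, t = 0.87: 1,312 × 0.87 = 1,141 exposed person-years, against 2,624 planned. E = 66 + 134 = 200. Simulated power 0.59 to 0.62.
- Malignancy, t = 2.24: 3,195 × 2.24 = 7,157 exposed person-years, against 15,975 planned. E = 67 + 134 = 201 (202 before rounding the parts). Simulated power about 0.61.
- With the full forecasts of 1,435 and 3,506 users, power is still only about 0.62 to 0.64.

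**5. Sensitivity to the last calendar year.** Step 3 counts all 2025 (serious infections) and 2028 (malignancy) initiators, as the protocol's totals do, although enrolment closes on 30 April 2025 and 31 May 2028. Prorating that year gives:

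- Malignancy: about 3,222 users with mean 2.42 years. The target of 3,195 is still met; 3,195 users give about 218 events and power 0.63.
- Serious infections: mean about 1.14 years but only about 1,011 users, so here the count itself would flag a shortfall. Total person-time barely moves (about 1,149 against 1,254 person-years).

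**The case against.** **The rule is soft.** The final reports are planned on condition that the sizes are reached; the text does not order finalisation once they are. Mitigation is only to be considered, and nothing forbids an extension if events are few. This stands. A reader might infer that reaching the user count automatically releases the report; the wording does not say so. What remains is that the size check itself gives no signal.

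**Events will be visible.** Section 10.2.1 justifies the study end by the need for enough outcomes, Section 10.7.1.2 tabulates events and asks for caution when they are few, and both interim reports carry descriptive analyses. So calling the user count the only safeguard would go too far. But none of these sets a threshold or feeds the decision.

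**Incidence could run higher.** The 39.8 rate comes from hospitalisations with infection as primary diagnosis; this study also counts secondary diagnoses, IV antimicrobials and deaths. That is fair, and it is a reason to watch events. The general-population rate of 9.6 would take power to about 45% at 1,312 users, but the protocol offers it as a bound, and it should not be read as a forecast for uncontrolled moderate to severe SLE.

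**Outcome capture.** A reader might infer from Section 10.9 that malignancies are under-captured in several countries. It says so only for France. For Germany and Spain it describes misclassification that could add cases, and Denmark has a cancer register. The German and Danish gaps concern serious infections.

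**A fixed event number is not a complete target.** Random-effects power also depends on how events are spread. With 450 events it is about 0.80 with the Table 13 shares, 0.73 if one source holds 90%, and 0.87 with four equal sources. This stands, and it argues for recomputing the target whenever the source mix changes and against simply swapping the user count for an event range.

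**The follow-up assumption is a separate error.** It could be corrected by itself. But a size check that ignores person-time would still miss any later departure.

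**Conclusion.** The point holds. The protocol measures study size in users, while its 80% power rests jointly on users, incidence, follow-up and matching. Under its own calendar, the user targets can be met with about 200 events per outcome against about 450, and power of about 60% against 80%, with no call for mitigation from the size check.

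The figures rest on the protocol's SLE incidence rates, full 1:3 matching, equal follow-up in both groups, the Table 27 uptake forecast, and no discontinuation, death or disenrolment; allowing for those losses would shorten follow-up further. Prorating the last enrolment year moves malignancy to 2.4 years and 63%. For serious infections it brings the user count below target, so there the check would work. Neither restores the planned events.

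**What to change.** In Sections 7, 10.4 and 10.5.2:

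1. Keep the user targets, but state that they count exposed patients in the matched cohorts.
2. Add pooled first events to the check at interim report 1, and at interim report 2 for malignancy. Count both groups together in the matched cohorts, after latency for malignancy.
3. Project events to the planned cut-off and compare them with the total implied by the protocol's calculation: about 450 per outcome at HR 1.5 and about 400 at HR 1, with the Table 13 shares. Recompute this if the source mix changes.
4. If the projection falls short, either consider the mitigation already listed in Section 10.4, or restate the achievable power in Section 10.5.2 and in the final report.

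The edit itself is small: descriptive analyses of the primary objectives are already planned for both interim reports, and combined counts give no between-group comparison. The consequences may be larger. On the protocol's own calendar the projection would probably fall short, so a final-report date may move, a back-up source may be needed, or the stated power will become less favourable.

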8 RATIONALE AND BACKGROUND

8.1 Disease burden of SLE

Systemic Lupus Erythematosus (SLE) is a chronic, multisystemic, autoimmune rheumatic disorder with a disease course characterised by periods of exacerbations and reduced activity or less commonly remission [71]. The multisystem disease is characterised by the production of autoantibodies and the occurrence of tissue damage resulting from inflammation and deposition of immune complexes as well as SLE-specific treatments [73]. There is significant heterogeneity in the clinical and biological manifestations with variable involvement of multiple organ systems including the skin, joints, kidneys, neurological and haematological systems. The fluctuating time course and diverse manifestations of SLE can lead to delays in diagnosis [73].

Epidemiological studies on SLE show marked gender, age, racial, temporal, and regional variations. Women are disproportionally more affected than men, with estimated female: male ratios ranging from 8:1 to 15:1 and peak incidence occurring between the ages of 15 and 45 years [71, 73]. Disease burden is estimated to be 2 to 3 times higher in people of African and Asian descent compared to people of Caucasian descent [70].

Globally, the incidence of SLE ranges from 0.3 to 23.7 cases per 100,000 person-years [71]. In the European Union (EU) and the United States of America (USA), incidence of SLE is estimated to range from 3.3 to 5.0, and 1.8 to 23.7 per 100,000 person-years [71] respectively. Prevalence estimates of SLE are 6.5 to 178.0 per 100,000 persons globally, 40.0 to 143.7 per 100,000 persons in the USA and 25.4 to 91.0 per 100,000 persons in Europe [71]. The prevalence of SLE has been increasing in recent years in the USA and in the United Kingdom (UK) [74, 96].

SLE is a complex, heterogenous disease with unknown aetiology. Identified risk factors include inherent genetic susceptibility, environmental triggers (sunlight/ultraviolet light, infection, smoking, alcohol), and immune system dysregulation [17, 21, 24, 61, 62].

8.2 Current treatment paradigm

Given the individual variability in SLE manifestations, there is no single treatment paradigm. A tailored, multidisciplinary strategy is required which needs to be adjusted to patients' individual clinical manifestations. The 2019 update of the European League Against Rheumatism (EULAR) recommendations for the management of SLE advises that treatment goals include long-term survival, prevention of organ damage, and optimisation of health-related quality of life [33].

For mild disease, first line treatments include antimalarials (e.g., hydroxychloroquine) and oral glucocorticoids (e.g., prednisone). Treatment options for moderate to severe disease and refractory disease (in addition to antimalarials and glucocorticoids) include conventional synthetic immunosuppressants (methotrexate, azathioprine, mycophenolate mofetil, and cyclophosphamide), calcineurin inhibitors, and more recently biologics such as anifrolumab and

belimumab. Rituximab (and it is biosimilars) are considered in severe, organ-threatening refractory cases [33].

Excluding the biologics, current therapy options are non-specific and inhibit broad inflammatory pathways that are not always relevant to SLE pathogenesis, leading to significant toxicity and organ damage [57]. Long-term use of hydroxychloroquine can cause retinopathy and poor adherence to treatment remains an issue with this drug [33]. Glucocorticoids are powerful immunosuppressant and anti-inflammatory agents that remain a mainstay of treatment for mild to severe disease [4]. Although glucocorticoids provide benefits in SLE, over time, organ damage from glucocorticoid use increases. Chronic glucocorticoid use is a contributing factor in long-term morbidity and early cardiovascular mortality [1, 68, 77] and the risk of irreversible organ damage increases with glucocorticoid dose [69, 90]. The use of non-specific conventional immunosuppressants is associated with an increased risk of infection, malignancy, and cardiovascular disease [8, 40, 41, 82]. Furthermore, these conventional immunosuppressants are not effective in all patients for all manifestations of SLE.

In the EU, belimumab and anifrolumab are the only medicines approved for SLE in the last 60 years since hydroxychloroquine was approved for use in discoid lupus and SLE. Belimumab, a neutralising anti-B-lymphocyte stimulatory monoclonal antibody, was approved by the European Medicines Agency in 2011, for the treatment of adult patients with active, autoantibody-positive SLE with a high degree of disease activity (e.g., positive anti- double stranded deoxyribonucleic acid and low complement) despite standard therapy. It targets one pathway, while patients are likely to have different underlying immunopathological pathways driving their SLE disease manifestations [26]. As such, it is not effective in all patients [7]. Anifrolumab, a human monoclonal antibody that binds to subunit 1 of the type 1 interferon receptor (IFNAR1) which was developed based on the evidence supporting the role of type 1 interferon pathway in SLE [37], was approved in the EU, via a centralised procedure, in 2022 as an add-on therapy for the treatment of adult patients with moderate to severe, active autoantibody-positive SLE, despite standard therapy. This was based on clinical trial evidence from TULIP 1, TULIP 2 and Phase 2 MUSE which showed that monthly administration of anifrolumab led to a higher percentage of patients with a response, assessed with the British Isles Lupus Assessment Group-based Composite Lupus Assessment, compared to patients receiving placebo [38, 65].

8.3 Serious infections and knowledge gaps

SLE patients have an intrinsically dysfunctional immune system which is exacerbated by disease activity that leaves them vulnerable to infection compared to the general population. Furthermore, treatment with immunosuppressive agents, even in the absence of other impairments of host defences, increases susceptibility to infection. This makes infections a major cause of morbidity and mortality among SLE patients.

Type 1 Interferons (IFN) are a fundamental innate defence system against viral infections. Largequantities of IFNs are produced during viral infections, resulting in the inhibition of viralCONFIDENTIAL AND PROPRIETARY24 of 130

replication. As anifrolumab binds to IFNAR1, blocks dimerisation of IFNAR2 and reduces the number of available IFNAR1 receptors, there may be a potential risk of increased susceptibility to infections during treatment on anifrolumab.

In placebo controlled clinical trials, patients exposed to anifrolumab showed higher frequency of infections when compared with placebo, particularly upper respiratory tract infections (34.4% vs. 23.2%), bronchitis (10.7% vs. 5.2%), herpes zoster (6.1% vs. 1.3%) and respiratory tract infection (overall) (3.3% vs. 1.5%) [29]. The majority of the infections in patients exposed to anifrolumab were mild or moderate in intensity. In addition, patients exposed to anifrolumab showed lower frequency of non-opportunistic serious infections when compared with placebo (4.8% vs. 5.6%) [92]. In phase III long term safety data, the most common non-opportunistic serious infection was pneumonia in both the anifrolumab and the placebo group. Pneumonia was also the commonest cause of fatal infections [28].

